3.2.6 Comorbid conditions

Patients with a history of any of the following contraindications to oxybutynin are not eligible: gastroparesis or gastrointestinal obstructive disorders; severe constipation defined as 2 or fewer bowel movements per week; significant gastric reflux symptoms not controlled by medication; ulcerative colitis; narrow-angle glaucoma; hypersensitivity to oxybutynin or any other components of the product; current uncontrolled hyperthyroidism; uncontrolled coronary artery disease or a history of myocardial infarction within the prior 12 months; NYHA Class II-IV congestive heart failure; symptomatic cardiac arrhythmias; current uncontrolled hypertension (average systolic >140 mm Hg and diastolic >90 mm Hg); myasthenia gravis; Parkinson's disease; or dementia.

- 3.2.7 Patients with urinary retention requiring indwelling or intermittent selfcatheterization within the prior 6 months are not eligible.
- **3.2.8 IPSS (Appendix III)** score < 20, unless they have a post void residual confirmation of less than 300 cc residual in the bladder (that is that the patient is eligible with a higher IPSS score if a subsequent PVR test looks good).
- **3.2.9** Life Expectancy of greater than 6 months.
- \_\_\_\_ 3.2.10 Age ≥ 18 years
- \_\_\_\_ 3.2.11 ECOG Performance Status- 0, 1, or 2
- \_\_\_\_\_ **3.2.12 Language:** In order to complete the mandatory patient-completed measures, participants must be able to speak and/or read English.
  - 3.2.13 Required Initial Laboratory Values: None

#### 4.0 PATIENT REGISTRATION

#### 4.1 Investigator and Research Associate Registration with CTEP

Food and Drug Administration (FDA) regulations and National Cancer Institute (NCI) policy require all individuals contributing to NCI-sponsored trials to register and renew their registration annually. To register, all individuals must obtain a Cancer Therapy Evaluation Program (CTEP) Identity and Access Management (IAM) account at In addition, persons with a registration type of Investigator (IVR), Non-Physician Investigator (NPIVR), or Associate Plus (AP) must complete their annual registration using CTEP's web-based Registration and Credential Repository (RCR) at

RCR utilizes five person registration types.

- IVR MD, DO, or international equivalent;
- NPIVR advanced practice providers (e.g., NP or PA) or graduate level researchers (e.g., PhD);
- AP clinical site staff (e.g., RN or CRA) with data entry access to CTSU applications such as the Roster Update Management System [RUMS], OPEN, Rave, acting as a primary site contact, or with consenting privileges;
- Associate (A) other clinical site staff involved in the conduct of NCI-sponsored trials; and
- Associate Basic (AB) individuals (e.g., pharmaceutical company employees) with limited access to NCI-supported systems.

RCR requires the following registration documents:

Documentation Required	IVR	NPIVR	AP	Α	AB
FDA Form 1572	$\checkmark$	$\checkmark$			
Financial Disclosure Form	$\checkmark$	$\checkmark$	$\checkmark$		
NCI Biosketch (education, training, employment,	$\checkmark$	$\checkmark$	$\checkmark$		
license, and certification)					
GCP training	$\checkmark$	$\checkmark$	$\checkmark$		
Agent Shipment Form (if applicable)	$\checkmark$				
CV (optional)	$\checkmark$	$\checkmark$	$\checkmark$		

An active CTEP-IAM user account and appropriate RCR registration is required to access all CTEP and Cancer Trials Support Unit (CTSU) websites and applications. In addition, IVRs and NPIVRs must list all clinical practice sites and Institutional Review Boards (IRBs) covering their practice sites on the FDA Form 1572 in RCR to allow the following:

- Addition to a site roster;
- Assign the treating, credit, consenting, or drug shipment (IVR only) tasks in OPEN;
- Act as the site-protocol Principal Investigator (PI) on the IRB approval; and
- Assign the Clinical Investigator (CI) role on the Delegation of Tasks Log (DTL).

In addition, all investigators acting as the Site-Protocol PI (investigator listed on the IRB approval), consenting/treating/drug shipment investigator in OPEN, or as the CI on the DTL must be rostered at the enrolling site with a participating organization.

Additional information is located on the CTEP website at For questions, please contact the RCR Help Desk by email at

#### 4.2 CTSU Site Registration Procedures

Permission to view and download this protocol and its supporting documents is restricted and is based on person and site roster assignment housed in the CTSU Regulatory Support System (RSS).

This study is supported by the NCI Cancer Trials Support Unit (CTSU).

#### **IRB** Approval

For CTEP and Division of Cancer Prevention (DCP) studies open to the National Clinical Trials Network (NCTN) and NCI Community Oncology Research Program (NCORP) Research Bases after March 1, 2019, all U.S.-based sites must be members of the NCI Central Institutional Review Board (NCI CIRB). In addition, U.S.-based sites must accept the NCI CIRB review to activate new studies at the site after March 1, 2019. Local IRB review will continue to be accepted for studies that are not reviewed by the CIRB, or if the study was previously open at the site under the local IRB. International sites should continue to submit Research Ethics Board (REB) approval to the CTSU Regulatory Office following country-specific regulations.

Sites participating with the NCI CIRB must submit the Study Specific Worksheet for Local Context (SSW) to the CIRB using IRBManager to indicate their intent to open the study locally. The NCI CIRB's approval of the SSW is automatically communicated to the CTSU Regulatory Office, but sites are required to contact the CTSU Regulatory Office at to establish site preferences for applying NCI CIRB approvals across their Signatory Network. Site preferences can be set at the network or protocol level. Questions about establishing site preferences can be addressed to the CTSU Regulatory Office by email or calling

In addition, the Site-Protocol Principal Investigator (PI) (i.e. the investigator on the IRB/REB approval) must meet the following criteria in order for the processing of the IRB/REB approval record to be completed:

- Holds an active CTEP status;
- Active status at the site(s) on the IRB/REB approval (*applies to US and Canadian sites only*) on at least one participating organization's roster;
- If using NCI CIRB, active on the NCI CIRB roster under the applicable CIRB Signatory Institution(s) record;
- Includes the IRB number of the IRB providing approval in the Form FDA 1572 in the RCR profile;
- Lists all sites on the IRB/REB approval as Practice Sites in the Form FDA 1572 in the RCR profile; and
- Holds the appropriate CTEP registration type for the protocol.

#### 4.2.1 Additional Requirements

Additional site requirements to obtain an approved site registration status include:

- An active Federal Wide Assurance (FWA) number;
- An active roster affiliation with the Lead Protocol Organization (LPO) or a Participating Organization (PO);
- An active roster affiliation with the NCI CIRB roster under at least one CIRB Signatory Institution (US sites only); and
- Compliance with all protocol-specific requirements (PSRs).

#### 4.2.2 Protocol specific requirements for A222001 site registration

#### Limited access information

This is a limited access study. Institutions that are interested in participating in this study must first contact **section 14.1** for instructions regarding how to be added to this trial.

#### 4.2.3 Downloading Site Registration Documents

Download the site registration forms from the protocol-specific page located on the CTSU members' website. Permission to view and download this protocol and its supporting documents is restricted to institutions and its associated investigators and staff on a participating roster. To view/download site registration forms:

- Log in to the CTSU members' website using your CTEP-IAM username and password;
- Click on *Protocols* in the upper left of the screen:
  - Enter the protocol number in the search field at the top of the protocol tree; or
  - Click on the By Lead Organization folder to expand, then select [Alliance], and protocol number [A222001].

Click on *Documents, Protocol Related Documents, and* use the *Document Type* filter and select *Site Registration to* download and complete the forms provided. (Note: For sites under the CIRB, IRB data will load automatically to the CTSU.)

#### 4.2.4 Submitting Regulatory Documents

Submit required forms and documents to the CTSU Regulatory Office using the Regulatory Submission Portal on the CTSU members' website.

To access the Regulatory Submission Portal log in to the CTSU members' website, go to the *Regulatory* section and select *Regulatory Submission*.

Institutions with patients waiting that are unable to use the Regulatory Submission Portal should alert the CTSU Regulatory Office immediately by phone or email: in order to receive further instruction and support.

#### 4.2.5 Checking your site's registration status

Site registration status may be verified on the CTSU members' website.

• Click on *Regulatory* at the top of the screen;

- Click on Site Registration; and
- Enter the sites 5-character CTEP Institution Code and click on Go.
  - Additional filters are available to sort by Protocol, Registration Status, Protocol Status, and/or IRB Type.

Note: The status shown only reflects institutional compliance with site registration requirements as outlined within the protocol. It does not reflect compliance with protocol requirements for individuals participating on the protocol or the enrolling investigator's status with NCI or their affiliated networks.

#### 4.3 Patient Registration Requirements

#### 4.3.1 Informed consent

The patient must be aware of the neoplastic nature of his/her disease and willingly consent after being informed of the procedure to be followed, the experimental nature of the therapy, alternatives, potential benefits, side-effects, risks, and discomforts. Current human protection committee approval of this protocol and a consent form is required prior to patient consent and registration.

This study includes the use of the mandatory patient completed measures. The patient reported measures are available in English. Participation in Alliance A222001 is restricted to patients who are able to speak, understand and read English.

#### **Patient questionnaire booklets**

Patient questionnaire booklets are to be ordered prior to the registration of any patients. Patient completed booklets can be ordered by downloading and completing the CTSU supply request form (located under the site registration documents section of the A222001 CTSU web site) and submitting it through the CTSU regulatory portal. Samples of the booklets are found in Appendices I-VII, which are to be used for reference and IRB submission only. They are not to be used for patient completion.

#### 4.4 Patient Enrollment (registration/randomization procedures (Step 1))

The Oncology Patient Enrollment Network (OPEN) is a web-based registration system available on a 24/7 basis. OPEN is integrated with CTSU regulatory and roster data and with the LPOs registration/randomization systems or the Theradex Interactive Web Response System (IWRS) for retrieval of patient registration/randomization assignment. OPEN will populate the patient enrollment data in NCI's clinical data management system, Medidata Rave.

Requirements for OPEN access:

- A valid CTEP-IAM account;
- To perform enrollments or request slot reservations: Must be on an LPO roster, ETCTN corresponding roster, or participating organization roster with the role of

Registrar. Registrars must hold a minimum of an Associate Plus (AP) registration type;

- If a Delegation of Tasks Log (DTL) is required for the study, the registrars must hold the OPEN Registrar task on the DTL for the site; and
- Have an approved site registration for the protocol prior to patient enrollment.

To assign an Investigator (IVR) or Non-Physician Investigator (NPIVR) as the treating, crediting, consenting, drug shipment (IVR only), or receiving investigator for a patient transfer in OPEN, the IVR or NPIVR must list the IRB number used on the site's IRB approval on their Form FDA 1572 in RCR. If a DTL is required for the study, the IVR or NPIVR must be assigned the appropriate OPEN-related tasks on the DTL.

Prior to accessing OPEN, site staff should verify the following:

- Patient has met all eligibility criteria within the protocol stated timeframes; and
- All patients have signed an appropriate consent form and Health Insurance Portability and Accountability Act (HIPAA) authorization form (if applicable).

Note: The OPEN system will provide the site with a printable confirmation of registration and treatment information. You may print this confirmation for your records.

Access OPEN at or from the OPEN link on the CTSU members' website. Further instructional information is in the OPEN section of the CTSU website at For any additional questions, contact the CTSU

Help Desk at

#### 4.5 Stratification Factors and Treatment Assignments

The randomization routine is found in Section 13 (Statistical Considerations).

#### 4.5.1 Stratification Factors

Stratification factors include:

4.5.1.1 Daily hot flash frequency at baseline: 4 to 9 hot flashes per day versus 10 or more hot flashes per day

4.5.1.2 Hot flash duration at baseline: less than 9 months versus 9 or more months, and

4.5.1.3 Number of prior hot flash therapies (0 versus 1 or more).

#### 4.5.2 Treatment Assignments

The factors defined in Section 4.5.1 will be used as stratification factors.

After the patient has been registered into the study, the values of the stratification factors will be recorded, and the patient will be assigned to one of the following treatment groups using the Pocock and Simon dynamic allocation procedure [41] which balances the marginal distributions of the stratification factors between the treatment groups.

- Oxybutynin: 2.5 mL oral BID Days 8 through 49 (total of 42 days)
- Oxybutynin: 5 mL oral BID Days 8 through 49 (total of 42 days)
- Placebo: 2.5 mL oral BID Days 8 through 49 (total of 42 days)
- Placebo: 5 mL oral BID Days 8 through 49 (total of 42 days)

Note: Oxybutynin concentration = 1mg/mL.

#### 4.6 **Procedures for Double-Blinding the Treatment Assignment**

After the treatment assignment has been ascertained by randomization, the Registration Specialist will notify the designated unblinded data manager/nurse/pharmacist at the patient's institution. The name of this designated unblinded contact person is to be indicated in the OPEN registration system at the time of registration. **This contact person may not be involved in assessing adverse events or any other outcome measure** and should not be the same person listed on page one of the OPEN registration form as the person completing the form. The OPEN registration form should provide the source of communication, either fax or e-mail, and the appropriate contact information. The Registration Specialist will then communicate the treatment assignment "Oxybutynin 2.5 mL, Placebo 2.5 mL, Oxybutynin 5 mL or Placebo 5 mL" to designated contact at the patient's institution.

Once the treatment assignment has been communicated, the designated contact should prepare the dose of drug or placebo for delivery to the patient.

The dose will be prepared and labeled as "oxybutynin/placebo" so that the contents are not discernible to the person administering the treatment.

The pharmacist or designated contact person will maintain records that indicate the identity of the patient and their corresponding treatment assignment. The pharmacist or designated contact person at the treating site will maintain records that indicate the identity of the patient and their corresponding study medication code number.

#### 4.7 Cross-Over Re-registration (step 2) Procedures

Patients who complete 6 weeks of study treatment and submit their questionnaires will be unblinded per the unblinding procedures in Section 8.3.2. In order to unblind the patient, site staff must call the Alliance Registration Office [contact]) during regular business hours to find out if the patient was receiving oxybutynin or placebo. Site staff must ensure that the questionnaires associated with the initial cycle of treatment have been completed and sent to the study staff by the patient before proceeding with unblinding, as these are related to the assessment of the primary endpoint of the study.

If the patient was receiving placebo, he will be allowed to cross over and receive oxybutynin at the discretion of the treating physician.

Patients who choose to enter the cross-over phase will be re-registered as follows:

- 1. Site staff will log into the OPEN registration system and select the appropriate patient.
- 2. Then select the next registration step. (Step 2)
- 3. Complete the OPEN Enrollment Form for the patient to be re-registered for the continuation phase. The patient will be re-registered to oxybutynin 2.5 or 5.0 mL, equivalent to whichever dose of placebo the patient was receiving prior to unblinding.
- 4. Verify the patient turned in their questionnaires for the initial cycle of treatment, yes/no.
- 5. Once the re-registration to the crossover phase is successfully completed, a confirmation email will be sent to the CRP.

If assistance is needed with this process, contact the Alliance Registration Office at

Following re-registration, the designated contact will be notified by the CRP so that s/he can prepare drug for delivery to the patient. Patient should be told that he may need to come back to the clinic to pick up open label supplies.

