#### 7.3 Patient Unblinding and optional crossover

Patients will be contacted on their last scheduled day of the study treatment. It should be assured that the patient has completed his questionnaires. Then the patient may be unblinded per the procedures described in Section 8.3.

If the patient was receiving placebo, he may choose to crossover to oxybutynin 2.5 or 5.0 mL, equivalent to whichever dose of placebo the patient was receiving prior to unblinding. This crossover will require a second registration (see Section 4.7 for re-registration instructions). The duration of treatment for patients who crossover will be 6 weeks.

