#### 8.3.2 Protocol-specified unblinding—Crossover Unblinding at end of treatment

The steps for unblinding a patient upon completion of study treatment are as follows:

- 1. Patient has completed 6 weeks of study treatment.
- 2. Site completes the form documenting end of treatment in Rave.
- 3. Site calls the registration office to unblind the patient; registration office confirms receipt of the end of treatment form with statistics and data center in order to communicate patient treatment assignment to site.

Contact the Alliance Registration Office at during regular business hours. Upon confirmation by the Primary Statistician (or designee) that the criteria for unblinding have been met, the treatment assignment may be unblinded. No Alliance Executive Officer (or designee) approval is required.

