#### 9.0 ADVERSE EVENTS

The prompt reporting of adverse events is the responsibility of each investigator engaged in clinical research, as required by Federal Regulations. Adverse events must be described and graded using the terminology and grading categories defined in the NCI's Common Terminology Criteria for Adverse Events (CTCAE), Version 5.0. The CTCAE is available at Attribution to protocol treatment for each adverse event must be determined by the investigator and reported on the required

forms. Please refer the NCI Guidelines: Adverse Event Reporting Requirements for further details on AE reporting procedures.

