#### **13.7.1** Adverse Event Stopping Rules

The stopping rules specified below are based on the knowledge available at study development. We note that the adverse event stopping rule may be adjusted in the event of either (1) the study re-opening to accrual or (2) at any time during the conduct of the trial and in consideration of newly acquired information regarding the adverse event profile of the treatment(s) under investigation. The study team may choose to suspend accrual because of unexpected adverse event profiles that have not crossed the specified rule below.

Accrual will be temporarily suspended to this study if at any time we observe adverse events considered at least possibly related to study treatment (i.e., an adverse event with attribute specified as "possible", "probable", or "definite") that satisfy either of the following:

- if 2 or more patients in the first 10 treated patients experience a grade 3 or higher adverse event felt to be attributed to the study agent and the event rate is higher in the treatment arms than the placebo arm.
- if after the first 10 patients have been treated, 10% of all patients experience a grade 3 or higher adverse event felt to be attributed to the study agent and the event rate is higher in the treatment arms than the placebo arm.

We note that we will review grade 4 and 5 adverse events deemed "unrelated" or "unlikely to be related," to verify their attribution and to monitor the emergence of a previously unrecognized treatment-related adverse event.

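### End-of-treatment unblinding does not wait for the week-6 adverse event assessment, so some blinded-period events could be graded and attributed with the arm known

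*Combined protocol and SAP*

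**What the plan says.** The conditions for releasing the arm at the end of treatment are spread over three sections.

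- Section 4.7 sets a condition for site staff to confirm: "questionnaires associated with the initial cycle of treatment have been completed and sent to the study staff by the patient before proceeding with unblinding". The reason given is the primary endpoint.
- Section 7.3: "Patients will be contacted on their last scheduled day of the study treatment", and "It should be assured that the patient has completed his questionnaires". Unblinding may follow.
- Section 8.3.2: step 1 is "Patient has completed 6 weeks of study treatment" and step 2 is "Site completes the form documenting end of treatment in Rave". The registration office confirms that the form has arrived, the statistician confirms that the criteria are met, and the assignment goes to the site. This list does not repeat the questionnaire condition.

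Section 4.6 restricts the person who prepares the drug: "This contact person may not be involved in assessing adverse events or any other outcome measure". No matching restriction covers staff who learn the arm at week 6.

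Adverse events are assessed by a nurse or coordinator in a call at the end of each treatment week (Section 5.0, Section 11.6, Appendix VII). Section 9.0 adds: "Attribution to protocol treatment for each adverse event must be determined by the investigator".

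**The concern.** The protocol keeps the one person who knows the arm during treatment away from adverse event assessment. At week 6 the arm goes to the site, whose nurse or coordinator makes the adverse event calls and whose investigator decides attribution. The last weekly call and the contact that can lead to unblinding fall at the same point, Day 49, and nothing fixes their order.

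Attribution is a judgement, and it has two consequences here. Under the Section 9.2 table, a grade 2 event requires routine submission only if it is at least possibly related. The Section 13.7.1 suspension rule counts only "adverse events considered at least possibly related to study treatment", and it also requires a higher rate on oxybutynin than on placebo. Staff who know the arm may lean towards calling oxybutynin events related and placebo events unrelated. That would tilt both the grade 2 record and the rule's between-arm comparison.

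**Working it through.** The plan gives no figure on this point, so there is none to reproduce. The check compares the passages and then sizes the effect under stated assumptions.

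**1. Is adverse event completion a release condition?** The full list is: six weeks of treatment completed (8.3.2), questionnaires completed and returned (4.7, 7.3), end-of-treatment form received (8.3.2), and statistician confirmation of the criteria (8.3.2). The re-registration steps in 4.7 also verify questionnaires only. None of these mentions adverse events.

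**2. Do the people overlap?** Site staff request the assignment (4.7). The coordinator receives the crossover confirmation (4.7) and is among those who make the weekly calls (Appendix VII). The investigator attributes (9.0).

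**3. How much of the blinded period is exposed?** Appendix VII has severity and attribution documented at each weekly call, so weeks 1–5 are largely recorded blind. Week 6 is 7 of 42 treatment days: 7/42 = 1/6, or 17%. I use f = 1/6 as the exposed share.

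**4. Grade 2 submission.** Assumptions, none from the documents: no true drug effect; 30% of men in each group have a grade 2 event; the chance that an event is attributed as at least possible is 50% when blinded, and 80% (oxybutynin) or 10% (placebo) when unblinded.

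- Oxybutynin: 0.30 × (5/6 × 0.50 + 1/6 × 0.80) = 0.165
- Placebo: 0.30 × (5/6 × 0.50 + 1/6 × 0.10) = 0.130
- Spurious gap: 3.5 points, or about one man in a group of 29 (29 × 0.035 = 1.0)

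**5. Suspension rule.** The 2:2:1:1 ratio puts 58 of 87 men on oxybutynin and 29 on placebo. With true grade 3 or higher rate r in every arm, the chance that a man has a counted event is:

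- blinded: r × 0.50
- oxybutynin, one sixth exposed: r × (5/6 × 0.50 + 1/6 × 0.80) = 0.550r
- placebo, one sixth exposed: r × (5/6 × 0.50 + 1/6 × 0.10) = 0.433r

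I simulated 200,000 trials per cell, with men in random order and the rule checked after each man: 2 or more counted events within the first 10, then 10% of all, each with the oxybutynin rate above placebo.

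| True grade 3+ rate | Suspended, all blinded | Suspended, one sixth exposed | Rise (points) |
|---|---|---|---|
| 1% | 0.3% | 0.3% | 0.0 |
| 2% | 0.9% | 1.1% | 0.2 |
| 3% | 2.0% | 2.4% | 0.4 |
| 6% | 8.2% | 9.5% | 1.3 |
| 10% | 21.4% | 24.9% | 3.4 |

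Section 13.4 expects the grade 3 or higher proportion to be very low, so the upper rows fit the plan best. Rises are taken from unrounded values.

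**The case against.** The strongest reply is that the ordinary sequence already protects the data. The week-6 call falls on or about Day 49. Release then needs returned questionnaires, often by mail, a form in Rave, two confirmations and a business-hours telephone call. Men who stop early for toxicity do not meet step 1 of Section 8.3.2, and unblinding is optional. Serious grade 3 events need an expedited report within 10 days (Section 9.3.1), so those that a site learns of by Day 39 (49 − 10) are due by Day 49. Section 13.7.1 also provides for review of grade 4 and 5 events called unrelated or unlikely. Form due dates sit in the Data Submission Schedule, and neither it nor the end-of-treatment form is shown. An adverse event check in either cannot be ruled out.

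Most of this stands, and it limits the size. The simulation exposes one sixth of every man's grade 3 or higher events, early stoppers included, so it leans high for that share. It does not close the gap: a likely order is not a required one, and attribution on the case report form can still be completed after release.

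A reader might infer that most adverse events could be attributed unblinded, or that related placebo events vanish. The documents do not support either reading. Appendix VII calls for weekly records of severity and attribution, with no grade threshold for recording side effects.

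**Conclusion.** The gap is real on the stated text and its likely effect is small. It concerns week-6 events and any blinded-period event whose investigator attribution is completed late. Under the assumed attribution rates with one sixth of events exposed, it could produce a 3.5-point spurious gap in submitted grade 2 events at a 30% event rate. Wrongful suspension would rise by under 0.5 point at grade 3 or higher rates of 1–3%, and by about 1 to 3 points at 6–10%. The attribution and event rates are assumptions.

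A reader might go further and conclude that the efficacy result or the planned by-arm safety summary is compromised. That does not follow. The hot flash diaries and Symptom Experience Questionnaires fall inside the questionnaire condition. The grade 3 or higher proportion in Section 13.4 ignores attribution, so only grading could shift it. No by-arm grade 2 comparison is specified, although grade 2 capture feeds the adverse event profile in objective 2.2.2. The change is worth making because it is cheap and applies the principle of Section 4.6 to the end of treatment.

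**What to change.** Add to Section 4.7 and to the numbered steps in Section 8.3.2 that, before the assignment is released:

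- the week-6 adverse event call has been made; and
- every adverse event from registration through the last blinded dose that needs routine reporting is in Rave with onset date, grade and investigator attribution.

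The registration office would check this together with the end-of-treatment form. Later entries or changes for the blinded period stay possible, but are flagged as made after unblinding, with a reason. Add the questionnaire condition to the 8.3.2 steps at the same time, so that the three sections agree. Emergency unblinding under Section 8.3.1 is untouched. If the end-of-treatment form or the Data Submission Schedule already enforces this, a sentence saying so is enough.

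The cost is one extra form check at a step where a form is already confirmed, and possibly a short delay to crossover at slow sites. No patients, visits or staff are added. Events that arise after unblinding, within the 30-day window of Section 9.2, will still be assessed with the arm known.
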